9.3 Selection of Study Population

9.3.1 Inclusion criteria

1. Male and female adults aged ≥ 40 years
2. Written informed consent obtained prior to any study-related procedure
3. Presence of an active exacerbation of the ongoing COPD requiring hospitalisation for treatment:

*“A sustained worsening of the patient’s condition (dyspnoea, cough and/or sputum production/purulence), from the stable state and beyond normal day-to-day variations, that is acute in onset and necessitates a change in regular medication in a patient with underlying COPD that includes prescriptions of systemic corticosteroids and/or antibiotics **and** need for hospitalisation”.*

4. Subjects with a diagnosis of COPD with spirometry performed outside an exacerbation within the last 12 months prior to the Screening Visit
5. Current smokers or ex-smokers with a smoking history of at least 10 pack years (pack-years = [number of cigarettes per day x number of years/20])
6. A FEV1 < 65% of the predicted normal value
7. A **documented** history of at least one moderate or severe COPD exacerbation in the 12 months preceding the Screening Visit that required antibiotics and/or systemic corticosteroid (addition or increment on subject current use) as defined below:
 - *“A sustained worsening of the patient’s condition (dyspnoea, cough and/or sputum production/purulence), from the stable state and beyond normal day-to-day variations, that is acute in onset and necessitates a change in regular medication in a patient with underlying COPD that includes prescriptions of systemic corticosteroids and/or antibiotics **or** need for hospitalisation”*
 - Also, documented visits to an emergency department due to COPD exacerbation are considered acceptable to fulfil this criterion.
8. Current regular treatment for COPD (categories C and D according to GOLD guidelines, updated 2015) for at least 2 months prior to the Screening Visit with either:
 - Inhaled corticosteroids/long-acting β_2 -agonist combination, long-acting muscarinic antagonist without regular use of any short-acting bronchodilator (any short-acting bronchodilator allowed if used as needed [PRN]) or
 - Inhaled corticosteroids/long-acting β_2 -agonist combination, without regular use of any short-acting bronchodilator (any short-acting bronchodilator allowed if used PRN or

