- 7 There will be sparse PK sampling in all subjects to be taken on any 2 of the 3 dosing occasions (Days 1, 3, or 5): one sample to be taken pre-dose, one sample taken 0-2 h post-dose, one sample taken 4-8 hours post-dose, and one sample no earlier than 12 hours post-dose. ECG will be taken at approximately the same time as with PK sample. ECGs should be taken before the PK sample.

A Symbol of Excellence

Statistical Analysis Plan (SAP)

- 8 Spirometry will be taken 'on bronchodilator' and ideally in the morning. For an individual spirometry should be taken at approximately the same time of day (during the acute phase \pm 1 hour and in the stabilisation phase \pm 2 hour window). Ideally this will be taken at least 1 hour after regular long acting bronchodilators and 30 minutes after short acting bronchodilator medication. Time of last short and long acting bronchodilators will be documented.
- 9 Spirometry at Screening should be performed 'on bronchodilator'. This will be taken after any regular long acting bronchodilator administration and 30 minutes after short acting bronchodilator medication.
- 10 Perform BMI and 6MWT at Day 14. BODE will then be calculated.
- 11 Please refer to the Laboratory Manual for clarification of whether the biomarker is to be analysed in either serum or plasma.
- 12 If the subject is discharged before Day 7, they will return to the hospital daily for assessment.
- 13 If screening and Day 1 occur on different days spirometry will be repeated on day 1 before dosing with study treatment and result obtained on day 1 may be used as baseline.
- 14 If historical spirometry data within last 12 months does not include pre and post SABA value this should be obtained during the stabilisation phase, for demographic purposes.
- 15 Physical examination at screening should include a minimum of chest, cardiovascular and abdominal examination. At all other time points a minimum of chest auscultation is required. Additional examination is at the discretion of the Investigator as indicated by the subjects' clinical condition.
- 16 A gynaecological history should be taken (from females only) with subjects specifically asked about vaginal bleeding, discharge or pain. Any new vaginal bleeding (other than normal menstruation), vaginal discharge or pain after dosing should be investigated by vaginal examination and any required specialist assessment.

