6.1 Intention-To-Treat population (ITT)

The ITT population includes all subjects who:

- Are randomised, and
- Receive at least one dose of study medication, and
- Provide a Baseline and at least one post-Baseline FEV1 value.

Patients will be included in the analysis per the treatment to which they were randomised.

Note: the 'Baseline' FEV1 value refers to the last non-missing FEV1 value assessed prior to the first dose of study medication.

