7.1.4.2 FEV1 normalisation

FEV1 normalisation is achieved if FEV1 returns to a value $\geq 89\%^3$ of the most recent FEV1 value measured within the last 12 months outside an exacerbation (pre-study FEV1 value).

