8.6.1 Analysis methods

Descriptive statistics will be presented for all endpoints. All statistical tests of the efficacy and exploratory endpoints will be two-sided tests and compared to a 5% significance level and all estimates will be presented with two-sided 95% CIs, unless otherwise specified.

Unless otherwise stated, all ANCOVA models and repeated measures models will include the baseline value (last non-missing value collected prior to the first dose of study medication) of the variable as covariate and treatment regimen, severity of airflow limitation at baseline (post-bronchodilator FEV1 at baseline (pre-dose) <30% or ≥30% of predicted normal value), blood eosinophils (%) value at baseline (<2% or ≥2%), time from start of current COPD exacerbation to first IMP dosing (≤2 days, 3-4 days or ≥5 days), presence of cardiovascular comorbidities at screening (yes, no) and COPD exacerbation treatment at screening (systemic corticosteroids only, antibiotics only or both systemic corticosteroids and antibiotics) as fixed effects. Repeated measures models will also include visit/inter-visit period, the treatment by visit/inter-visit period interaction and the baseline by visit/inter-visit period interaction. The adjusted mean difference between treatment regimens will be presented along with a two-sided 95% CI for the time-points of interest.

The calculation of the adjusted means (least squares means) will be based on:

- coefficients for classification effects (i.e., the effects of categorical covariates) proportional to the margins observed in the group of patients analysed;
- effects of quantitative covariates set equal to their mean values in the group of patients analysed.

See Appendix F for details on the calculation of adjusted means (least squares means).

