The number and proportion of patients normalised for FEV1 (i.e. FEV1 returns to a value $\geq 89\%$ of the most recent FEV1 value measured within the last 12 months outside an exacerbation) at each visit will be reported by treatment regimen and Pearson's Chi-square test (or Fisher's exact test as appropriate) will be applied to compare normalisation rates at each visit between treatment regimens (two-sided test at 5% alpha level).

Moreover, a bar chart will be presented per treatment regimen for the normalisation of FEV1 at each visit showing the percentage of subjects normalised compared with the most recent test performed within the last 12 months outside an exacerbation.

A similar analysis will be used for:

- Normalisation of FEV1/FVC (i.e. FEV1/FVC returns to a value $\geq 89\%$ of the most recent FEV1/FVC value measured within the last 12 months outside an exacerbation) at each visit.

The timepoints to consider for these analyses are Days 1 to 7, Days 10 and 14, and Weeks 8, 12 and 26.

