11 APPENDICES

Appendix A – Summary of Protocol Amendments - Key Changes

Amendment	Change	Rationale
Protocol Version 2.0, Amendment 1 (revisions to Protocol Version 1.0)	Added pulse oximeter measurements as part of vital sign measurements to be carried out	At the request of the FDA
Protocol Version 3.0, Amendment 2 (revisions to Protocol Version 2.0)	Laboratory test change: requirement for INR and prothrombin time sampling and testing after Day 14 removed	As the last dose is taken on Day 5, analysis of INR and prothrombin time is only deemed necessary during the Acute Exacerbation Phase
Protocol Version 3.0, Amendment 2 (revisions to Protocol Version 2.0)	Reduction of ECG testing from triplicate to a single test	ECG are no longer required in triplicate by the Central Reader
Protocol Version 3.0, Amendment 2 (revisions to Protocol Version 2.0)	Addition of inflammation of cervix and vagina as an adverse event of special interest	Align with Investigator's Brochure at the request of the UK Regulatory Agency
Protocol Version 4.0, Amendment 3 (revisions to Protocol Version 3.0)	Modification of inclusion criterion 4 to reflect that spirometry in the past 12 months is required but the result does not need to be available before dosing.	Spirometry is being done at screening and this will be used to determine eligibility for the study. Historical data is required for data analysis demography only. If historical values are not available, pre and post bronchodilator spirometry will be conducted during the stabilization phase, for demographic purposes.
Protocol Version 4.0, Amendment 3 (revisions to Protocol Version 3.0)	Modification of inclusion criterion 5 to allow subjects who have given up smoking in the last 6 months into the study.	The impact of smoking cessation within 6 months is not significant to the patient assessment, within the trial.
Protocol Version 4.0, Amendment 3 (revisions to Protocol Version 3.0)	Increase of FEV1 to <65 % of the predicted normal value for inclusion criterion 6.	This will facilitate recruitment of the appropriate population and is not anticipated to adversely impact safety of subjects or efficacy outcomes.

Protocol Version 4.0, Amendment 3 (revisions to Protocol Version 3.0)	Removal of inclusion criterion 7 regarding post-bronchodilator spirometry.	In the acute exacerbation setting it is challenging to conduct pre and post bronchodilator spirometry. Therefore, all spirometry measurements will be performed 'on bronchodilator'.

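### Spirometry normalisation is tested without adjusting for the pre-dose ratio to the pre-study value: no bias, but some precision may be lost, and the Day 1 test compares pre-dose values

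*SAP*

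**What the plan says.** SAP 7.1.4.2 counts FEV1 as normalised when it is at or above 89% "of the most recent FEV1 value measured within the last 12 months outside an exacerbation (pre-study FEV1 value"). SAP 7.1.4.3 applies the same rule to FEV1/FVC. Neither sets a condition on where the patient stood before the first dose.

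SAP 8.6.3.2 reports the proportion normalised per regimen, and a Pearson chi-square or Fisher test "will be applied to compare normalisation rates at each visit between treatment regimens". No covariate enters. On timing it says: "The timepoints to consider for these analyses are Days 1 to 7, Days 10 and 14, and Weeks 8, 12 and 26".

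The Day 1 spirometry is a pre-dose measurement. A footnote to the schedule of assessments says that, where screening falls on another day, "spirometry will be repeated on day 1 before dosing with study treatment and result obtained on day 1 may be used as baseline". SAP 8.1.7 takes the last spirometry before first intake as the Visit 1 value.

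Both parts of the pre-dose ratio are meant to be on file. ITT patients must "Provide a Baseline and at least one post-Baseline FEV1 value" (SAP 6.1), and Protocol 9.3.1 criterion 4 admits "Subjects with a diagnosis of COPD with spirometry performed outside an exacerbation within the last 12 months prior to the Screening Visit". SAP Appendix A adds that "spirometry in the past 12 months is required but the result does not need to be available before dosing", so a pre-study value may be missing for some patients.

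SAP 8.6.1 sets the covariate rule for modelled endpoints: "Unless otherwise stated, all ANCOVA models and repeated measures models will include the baseline value", together with five prognostic factors. Chi-square tests fall outside it.

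**The concern.** Whether a patient reaches 89% of the pre-study value at Day 7 depends strongly on how far below 89% that patient starts. No eligibility criterion requires a fall from the pre-study value; criterion 6 asks only for FEV1 below 65% of predicted. Some patients may therefore be at or above 89% before dosing and can count as successes. An unadjusted comparison leaves this variation in the error term, although the trial already holds the covariate that explains it. At stake is the chance of detecting a real difference in recovery on a named secondary endpoint.

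The Day 1 test is a separate, smaller matter. It compares randomised arms before any treatment and sits among the efficacy results.

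**Working it through.** **Plan's own figure.** Protocol 13.1 and SAP 5 give a 100 mL effect, SD 230 mL, two-sided 5% and 80% power. n per arm = 2 × (1.960 + 0.842)² × (230/100)² ≈ 83.1, so 84. The t-test gives 79.99% power at 84 and 80.5% at 85, which reproduces 85 per arm and 3 × 85 = 255. For dropout, 255/0.95 = 268.4, so 269, or 90 per arm for 270. The documents give no expected rate or power for normalisation.

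**Inputs for the check.** From the documents: effect 100 mL, SD of change 230 mL, 85 per arm, threshold 89%. Assumed: pre-study FEV1 mean 1.3 L (SD 0.4), pre-dose ratio mean 0.80 with SD 0.10 to 0.20, mean gain on standard of care 100 mL.

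**How strongly the start matters.** Take a placebo patient with pre-study FEV1 1.3 L. The threshold is 0.89 × 1.3 = 1.157 L.
- Ratio 0.65: pre-dose 0.845 L, needs +312 mL. P = 1 − Φ((312 − 100)/230) = 18%.
- Ratio 0.80: pre-dose 1.040 L, needs +117 mL. P = 1 − Φ((117 − 100)/230) = 47%.
- Ratio 0.95: pre-dose 1.235 L, needs −78 mL. P = 1 − Φ((−78 − 100)/230) = 78%.

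The assumed drug effect at ratio 0.80 moves 47% to 1 − Φ((117 − 200)/230) = 64%. If change is unrelated to the ratio, one SD of 0.15 either way matters more than treatment.

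**Normalised before dosing.** P(ratio ≥ 0.89) = 1 − Φ((0.89 − 0.80)/SD) gives 1 − Φ(0.90) = 18%, 1 − Φ(0.60) = 27% and 1 − Φ(0.45) = 33% for SD 0.10, 0.15 and 0.20.

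**Power at Day 7, FEV1, one pairwise comparison.** Simulation of the unadjusted two-proportion test against logistic regression with treatment and the continuous pre-dose ratio. Ranges are over repeated runs. With 1,500 trials the Monte Carlo standard error near 50% is √(0.25/1500) = 1.3 points.

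| SD of ratio | Unadjusted, change unrelated to ratio | Adjusted | Gain | Gain at correlation −0.4 | Gain at −0.6 |
|---|---|---|---|---|---|
| 0.10 | 49–51% | 55–56% | 5–6 | about 0 | about −1 |
| 0.15 | 40–42% | 50–51% | 8–10 | about 4 | about 1 |
| 0.20 | 33–34% | 44–46% | 11–12 | about 7–9 | about 6 |

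The correlation is between the pre-dose ratio and the subsequent change; negative means that patients who fell further recover more. Adding seven pure-noise covariates left the pattern unchanged.

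**Other assumptions.** With pre-study FEV1 1.2 L (SD 0.35), ratio mean 0.75 to 0.95 and SD 0.10 to 0.25, the gain was about 2 to 17 points and 8% to 73% were normalised before dosing. At ratio mean 0.85 and SD 0.15, power rose from 41% to 52% with recovery unrelated to the deficit, and from 53% to 60% with a recovery slope of 0.4 on the deficit. Type I error was 4.8–5.5% unadjusted and 4.8–5.4% adjusted.

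**What drives the gain.** A cross-check fixed the rates. For 0.40 v 0.55 at 85 per arm, unadjusted power is Φ((0.15 − 1.96 × √(2 × 0.475 × 0.525/85))/√((0.24 + 0.2475)/85)) = Φ((0.15 − 0.150)/0.0757) ≈ 50%. For 0.55 v 0.70 it is 52%. The gain then depends on the correlation between the pre-dose and visit ratios: about 0–2 points at 0.2 or below, 4–5 at 0.4, 6–8 at 0.5, 10–12 at 0.6 and 15–18 at 0.7. If the pre-dose state no longer predicts the ratio at Weeks 8 to 26, nothing is gained there.

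**Day 1.** The outcome is fully determined by the pre-dose ratio, so no adjusted model can be fitted, and under randomisation any difference is chance. Pairwise testing gives 2 parameters × 3 pairs = 6 such tests, of 12 × 2 × 3 = 72 per analysis population.

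**The case against.** Three stronger readings are tempting, and the documents do not support them.

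A reader might infer that counting already-normalised patients biases the comparison. It does not. Allocation is randomised 1:1:1, chance imbalance in the pre-dose ratio is already in the test's sampling error, and the simulated type I error is held. The cost is a diluted contrast and lower power.

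A reader might infer that 8.6.3.2 breaks a rule that every continuous model adjusts for baseline. There is no such rule. SAP 8.6.1 covers ANCOVA and repeated measures models. Steroid dose (8.6.4.3), BODE (8.6.4.6) and the subgroup comparisons (8.8.3) use unadjusted one-way ANOVA. Unadjusted tests of proportions are the SAP's convention: respiratory rate normalisation (8.6.3.5), exacerbations (8.6.3.11), COPD-related deaths (8.6.3.12) and treatment failure (8.6.4.1).

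A reader might infer that power is recovered for certain and free of charge. The size rests on inputs absent from the documents and can be nil. The fix also adds models and replaces a simple test.

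The strongest objection concerns importance. Baseline-adjusted FEV1 is already analysed by MMRM at Days 2 to 7 and ANCOVA at Days 3, 10 and 14, and FEV1/FVC by ANCOVA at Days 3, 7, 10 and 14. Protocol 13.5.1 treats all analyses as exploratory without multiplicity adjustment, so no decision rule hangs on this test. That stands and limits the weight of the point. It is also fair that tabulating Day 1 shows the pre-dose normalised proportion per arm, and that the protocol lists Day 1 for this endpoint; only the Day 1 p-value is uninformative.

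**Conclusion.** The point holds as one of efficiency. The unadjusted test is valid but leaves out a prognostic covariate available for every patient who can be classified for FEV1. FEV1/FVC also needs the baseline FVC. A patient without a pre-study value cannot be classified under either analysis, so adjustment loses no one for FEV1.

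At Day 7, 85 per arm and the assumed inputs, the gain in pairwise power is about 5 to 12 points if change is unrelated to the pre-dose ratio, and about 0 to 9 points at a correlation of −0.4 to −0.6. It may be nil at late visits. FEV1/FVC was not simulated, so no size is claimed for it.

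That the Day 1 between-arm test can show only chance follows from the text and randomisation, without these assumptions. Overall importance is modest.

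**What to change.** In SAP 8.6.3.2:

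- For post-dose visits, Day 2 onward, compare regimens by logistic regression with treatment and the continuous pre-dose ratio to the pre-study value, adding the 8.6.1 covariates where the model supports them. Use the FEV1 ratio for FEV1 and the FEV1/FVC ratio for FEV1/FVC.
- Report the odds ratio and the standardised risk difference, each with a 95% CI. The odds ratio is conditional on the covariates; the risk difference speaks to the proportions shown.
- Keep the planned proportions and bar chart. Show Day 1 as the pre-dose normalised proportion per regimen, without a p-value.
- State in advance the sparseness rule, for example a minimum event count, under which Fisher's exact test replaces the model.

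In the same edit, settle which chi-square is meant where one is retained: 8.6.3.2 names Pearson's test, while Appendix F heads its code as continuity-corrected. In the simulated scenarios the correction cost a further 5 to 9 points of unadjusted power.

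Cost: no new data. Protocol 13.5.3 prescribes no test for normalisation and leaves detail to the SAP, so no protocol change is implied. The work is 11 post-dose visits × 2 parameters × 2 populations (ITT and PP) = 44 models, and a model-based estimate takes the place of a simple test.

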8.6.3.3 Time to improvement in FEV1 value over time

8.6.3.3.1 Time to improvement of 100 mL in FEV1 over time

Time to improvement of 100 mL in FEV1 from baseline will be analysed using the Kaplan-Meier method. Patients without an improvement of 100 mL in FEV1 from baseline or who are discontinued before reaching it will be considered as "censored" patients.

For the study periods Day 1, Day 2, Day 3, Day 4, Day 5, Day 6, Day 7, Days 8-10, Days 11-14, Weeks 3-8, Weeks 9-12 and Weeks 13-26, the number of patients without an improvement of 100 mL in FEV1 from baseline at the beginning of the period, the cumulative number of patients with

an improvement of 100 mL in FEV1 at the end of the period and the probability of improvement of 100 mL in FEV1 at the end of the period with the associate two-sided 95% CIs will be presented by treatment regimen. The point estimates and the relative two-sided 95% CIs will be presented by treatment regimen for the 75th, 50th and 25th percentiles. A Kaplan-Meier plot will also be presented. Comparisons between treatment regimens will be performed by means of the log-rank test. The p-values of the pairwise log-rank test comparisons will be displayed on the figure.

See Appendix F for SAS code used to implement Kaplan-Meier method.

8.6.3.3.2 Time to improvement of 80 mL in FEV1 over time

A similar analysis as in Section 8.6.3.3.1 will be performed for the time to improvement of 80 mL in FEV1 from baseline over time.

8.6.3.4 Standardised AUC of FEV1 over time

The standardised AUCs of FEV1 (Day 1 to Day 3, Day 1 to Day 7, Day 1 to Day 10 and Day 1 to Day 14) will be derived and summarised with standard descriptive statistics by treatment regimen.

The standardised AUC from Day 1 to Day 14 will be analysed using an ANCOVA model estimating the effect up to Day 14, using OC, including treatment, severity of airflow limitation at baseline, blood eosinophils (%) value at baseline, time from start of current COPD exacerbation to first IMP dosing, presence of cardiovascular comorbidities at screening and COPD exacerbation treatment at screening as fixed effects and baseline FEV1 value as a covariate.

The ANCOVA model results will be presented with LSMEAN and standard error (SE) of each treatment regimen as well as the adjusted mean difference between treatment regimens at Day 14 and associated two-sided 95% CIs. Each pairwise treatment regimen comparison will be tested at an alpha level of 5%. P-values of the effects will also be presented.

A similar ANCOVA model will be used for analysis of:

- Standardised AUC of FEV1 from Day 1 to Day 7
- Standardised AUC of FEV1 from Day 1 to Day 10.

8.6.3.5 Normalisation of RR over time (daily from Days 1 to 7, 10 and 14)

The number and proportion of patients normalised for RR (i.e. RR returns to a plateau level, as defined in Section 7.1.4.6) at each visit during the Acute Exacerbation Phase will be reported by treatment regimen and Pearson's Chi-square test (or Fisher's exact test as appropriate) will be applied to compare normalisation rates at each visit between treatment regimens (two-sided test at 5% alpha level).

The timepoints to consider for these analyses are Days 1 to 7, Day 10 and Day 14.

8.6.3.6 Change in RR on Days 3, 7, 10 and 14

A descriptive summary table will be presented for RR absolute values and change from baseline on Days 3, 7, 10, and 14 by treatment regimen and visit.

A graphical representation of the RR distribution using mean plots (mean and SD) will be provided over time per treatment regimen. The three treatment regimens will be plotted on the same graph.

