13.4.2 Secondary Efficacy Endpoint(s)

Efficacy will be further assessed based on the following secondary endpoints:

1. Comparison of FEV1 on Days 3, 10, and 14
2. Normalisation evaluation of spirometry parameter (FEV1, FVC and FEV1/FVC) response over time (performed from Days 1 to 7, 10, 14, and at Weeks 8, 12 and 26) compared with the most recent test performed within the last 12 months outside and exacerbation (pre-study FEV1, FVC, and FEV1/FVC value)
3. Time taken to improvement of 100 mL in FEV1 compared to Baseline versus placebo
4. Comparison of AUC of FEV1 over time among groups
5. Change in RR over time (performed daily from Days 1 to 7, 10 and 14) among groups
6. Change in RR on Days 3, 7, 10 and 14 among groups
7. Time to improvement based on EXACT-PRO total score
8. Comparison of AUC of EXACT-PRO over time among groups
9. Number of COPD-related deaths during the study

10. Number of moderate/severe COPD-related exacerbations during the study
11. Time to next moderate/severe COPD exacerbation
12. Change from Baseline at each inter-visit period and over the entire period of the study in the average EXACT-PRO total score and domain scores
13. Number of times each subject required rescue therapy during the study
14. Time from hospitalisation until the subject is medically ready (COPD-related) for discharge
15. Nonlinear mixed effects PK/PD models evaluating the relationship between BCT197 exposure and efficacy/safety endpoints.

More details and the time points for collection are given in [Section 9.1.3](#) and in the Schedule of assessments ([Table 9-1](#)). A complete list of efficacy endpoints is given in [Section 11.2](#).

These secondary efficacy parameters will be assessed using the ITT population.

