13.5.3 Analysis of Secondary Endpoints

The analysis of secondary efficacy endpoints will be performed on the ITT population.

For the secondary efficacy endpoints, data will be summarised by treatment regimen and visit.

For each continuous parameter, change from Baseline will be assessed with a MMRM analysis, with treatment regimen as a factor and the Baseline value as a covariate. The adjusted mean difference between treatments will be presented along with a 95% confidence interval for the time-points of interest.

The proportion of subjects with a COPD-related death will be summarised and compared between treatment regimens using Fisher's Exact Test.

The pharmacokinetic parameters will be summarised by dose group and visit day.

A more detailed description will be presented in the SAP.

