7.1.4.6 Respiratory Rate (RR) normalisation

RR is normalised if RR returns to a baseline plateau level achieved after the acute COPD exacerbation during the Stabilisation Phase. This baseline plateau value is defined on a patient basis, and corresponds to the mean of the 3 RR values recorded during the Stabilisation Phase for each patient (mean of RR at Weeks 8, 12 and 26). Only 1 of the 3 data points needs to be present for this computation. In the case that all three RR values are missing during the Stabilisation Phase for a patient, the baseline plateau value will be set to 20 breaths/min².

To summarise, RR is normalised if RR returns to a value $\leq P$ breaths/min; where P (“Plateau”) equals to:

- mean of RR at Weeks 8, 12 and 26 (on a patient basis)
- 20 breaths/min, if all three RR values at Weeks 8, 12 and 26 are missing.

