8.6.4.5 Change from Baseline in mMRC dyspnoea scale over time

This exploratory endpoint will be analysed separately during the Acute Exacerbation Phase (from Study Day 1 until Day 14 included) and the Stabilisation Phase (from Day 14 until Week 26).

The mMRC dyspnoea scale (graded from 0 to 4) will be summarised at each visit by treatment regimen using descriptive statistics. Changes in mMRC dyspnoea scale from baseline (Visit 1 pre-dose) will be summarised at each post-baseline visit (Day 7 and Day 14) during the Acute Exacerbation Phase by treatment regimen. Changes in mMRC dyspnoea scale from baseline (Visit 9, Day 14) will also be summarised at each post-baseline visit (Weeks 8, 12 and 26) during the Stabilisation Phase by treatment regimen.

MMRM analysis using an unstructured covariance matrix and the Kenward-Roger adjustment for the denominator degrees of freedom will be performed for statistical comparison of treatment regimens with change in mMRC as an outcome. MMRM analyses will be done separately for the Acute Exacerbation Phase and for the Stabilisation Phase. Both models will consider treatment, severity of airflow limitation at baseline (pre-dose), blood eosinophils (%) value at baseline (pre-dose), time from start of current COPD exacerbation to first IMP dosing, presence of cardiovascular comorbidities at screening and COPD exacerbation treatment at screening as fixed effects and baseline mMRC (Visit 1 pre-dose for the Acute Exacerbation Phase, Visit 9/Day 14 for the Stabilisation Phase) as covariate. In addition the baseline mMRC-by-visit and the treatment-by-

visit interactions will be included in the model.

LSMEAN and standard error (SE) of each treatment regimen, difference of LSMEANS between treatment regimens and their associated two-sided 95% CIs and corresponding two-sided P-values for Day 7, Day 14 (Acute Exacerbation Phase) and Weeks 8, 12 and 26 (Stabilisation Phase) will be estimated by the model. P-values of the effects will also be presented.

The unstructured covariance matrix (which does not presume a particular correlation structure for repeated measurements within patients over time) will be used to adjust for the within-patient error variance covariance. In case model fails to converge, other covariance matrix structures will be considered in the sequence of Ante-dependence, Toeplitz, Heterogeneous AR(1), Heterogeneous Compound Symmetry, and Compound Symmetry.

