9 CHANGES TO PLANNED ANALYSIS FROM STUDY PROTOCOL

- **Definition of PP population:**
The PP definition stated in the protocol was clarified, in that only key inclusion/exclusion criteria with respect to factors likely to affect the assessment of efficacy need to be satisfied to include a subject in the PP population.
- **PP analyses:**
A PP analysis was added for the secondary and exploratory efficacy endpoints for this PoC and hypothesis-generating study. This PP analysis was initially planned in the study protocol on the primary efficacy endpoint only.
- **Cumulative oral/IV steroid dose analysis:**
The exploratory endpoint specified in the study protocol is “Cumulative oral/IV steroid dose from Day 1 to Day 14 and from Day 14 to Week 26”. This analysis was finally performed during the duration of current COPD exacerbation (i.e. from the date when symptoms started until the date when symptoms stopped) upon Mereo’s request. Sponsor was more interested in the amount of systemic steroids needed to control the current COPD exacerbation.

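### Change in respiratory rate (secondary endpoint 6) is only described in the SAP, although the protocol plans an MMRM with adjusted differences, and SAP section 9 does not list the change

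*SAP*

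**What the plan says.** Protocol 13.4.2 lists as its sixth secondary efficacy endpoint "Change in RR on Days 3, 7, 10 and 14 among groups". SAP 4.2 keeps the same endpoint under the same number.

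On method, Protocol 13.5.3 states "For each continuous parameter, change from Baseline will be assessed with a MMRM analysis", with treatment regimen as a factor and the Baseline value as covariate. The output is to be an adjusted mean difference between treatments with its 95% CI at the time-points of interest. The section leaves further detail to the SAP.

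SAP 8.6.3.6 deals with this endpoint in two short paragraphs. The first reads "A descriptive summary table will be presented for RR absolute values and change from baseline" on the four named days, by regimen and visit. The second adds a plot of means and SDs over time.

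Two general rules of the SAP also apply. SAP 8.1.4 says the three regimens will be compared pairwise on efficacy data. SAP 8.6.1 says that, unless otherwise stated, "all ANCOVA models and repeated measures models will include the baseline value" and then names a common set of fixed effects.

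SAP section 9, headed "CHANGES TO PLANNED ANALYSIS FROM STUDY PROTOCOL", has three entries: the PP definition, the added PP analyses and the period for cumulative steroid dose. None concerns RR.

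**The concern.** The protocol commits to an estimated treatment difference with an interval for this endpoint. The SAP as written would not produce one. A reader of the study report would get arm-level means and SDs, with no adjusted contrast and no pre-specified test. The section of the SAP meant to disclose such changes would give no sign that anything had been dropped.

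This matters more in a hypothesis-generating Phase IIa trial than the exploratory label suggests, because estimates with intervals are what such a trial is meant to supply. RR is not incidental either: the protocol synopsis names it beside FEV1 as a daily assessment in Part 1.

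**Working it through.** No arithmetic in the plan bears on RR. The sample size calculation (Protocol 13.1, SAP 5) is for FEV1 alone: difference 100 mL, SD 230 mL, two-sided 5%, power 80%. It reproduces (84.01 per arm by the t-test calculation, rounded up to the stated 85) but says nothing about RR. The check is therefore a comparison of the texts.

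1. **Does Protocol 13.5.3 cover the endpoint?** RR is continuous, the endpoint is a change from Baseline, and it has named days. It meets each condition of the 13.5.3 rule. The sentence in Protocol 13.5.2 that limits formal analysis to data up to Day 7 stands under the primary endpoint and concerns FEV1, so it does not remove Days 10 and 14 for RR.

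2. **Does SAP 8.6.3.6 supply the comparison?** No. It has a table and a plot, with no model, contrast, interval or p-value.

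3. **Is it supplied elsewhere in the SAP?**
   - SAP 8.6.1 fixes the contents of models that are used. It does not call for a model of RR.
   - SAP 8.7.3 summarises RR as a vital sign, again descriptively.
   - SAP 8.6.3.5 compares the proportion of patients with normalised RR by chi-square or Fisher's exact test. That is item 5 in SAP 4.2 and objective 5 in Protocol 8.2. It is a yes/no outcome and yields no difference in breaths/min.

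4. **How does the SAP treat comparable endpoints?**
   - Change in FEV1 on Days 3, 10 and 14 gets ANCOVA by visit (SAP 8.6.3.1).
   - Acute-phase EXACT-PRO gets an MMRM (SAP 8.6.3.7).
   - The exploratory dyspnoea scale gets an MMRM in each phase for "statistical comparison of treatment regimens with change in mMRC as an outcome" (SAP 8.6.4.5).
   - Change in RR, a secondary endpoint, gets none.

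5. **Is the departure disclosed?** No. Section 9 records a changed analysis window for an exploratory endpoint (steroid dose), so a dropped comparison for a secondary endpoint belongs there too.

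6. **Are the data available?** Yes. Protocol Table 9-1 schedules vital signs, including RR, at every visit. The post-baseline acute-phase visits are Days 2 to 7, 10 and 14, that is 6 + 2 = 8 visits. Three pairwise contrasts at four days give 3 × 4 = 12 adjusted differences per population.

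**The case against.** The best defence has four parts.

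- **The protocol defers to the SAP.** It promises more detail there. That allows the SAP to specify the model. It does not cover removing the planned estimate without saying so.
- **RR is still compared between arms.** This is true of normalisation, but it is a different endpoint on a different scale.
- **Little is lost.** The descriptive table gives n, mean and SD by arm and visit (SAP 8.1.3), so a reader can compute an unadjusted difference and interval. This stands. What is lost is the adjusted estimate and the pre-specified test.
- **RR is not the only unlisted departure.** This also stands. FEV1 on Days 3, 10 and 14 moves from MMRM to ANCOVA (SAP 8.6.3.1). Stabilisation Phase change in EXACT-PRO is descriptive only (SAP 8.6.3.10). FVC is dropped from the spirometry normalisation endpoint (Protocol 13.4.2 against SAP 4.2, item 2). An entry for RR alone would leave section 9 incomplete.

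A reader might go further and infer that the normalisation test is unsound because its threshold is measured after randomisation. The documents do not support that. SAP 7.1.4.6 openly defines the plateau as the "mean of the 3 RR values recorded during the Stabilisation Phase for each patient", with a fallback of "20 breaths/min, if all three RR values at Weeks 8, 12 and 26 are missing", so its timing is already clear. RR normalisation is a protocol objective, the schedule collects no pre-exacerbation RR to use instead, and nothing in the documents shows that later RR differs between arms. There is no ground here for changing that rule.

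**Conclusion.** The discrepancy holds: the protocol plans a between-group model for this endpoint, the SAP gives description only, and section 9 does not mention it. This rests on the text alone and needs no outside assumption.

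It should be corrected, but its weight is moderate. It concerns one of 15 secondary endpoints, there is no multiplicity control for it to disturb, Protocol 13.5.1 calls all analyses exploratory, and the FEV1 analysis at Day 7 is unaffected.

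A reader might also want a figure for lost power or precision. None can be derived, because neither document gives an SD or target difference for RR; any such number would only restate whatever was assumed. Nor do the documents show whether the omission was deliberate or an oversight.

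**What to change.** In SAP 8.6.3.6, keep the table and plot and add an MMRM of change in RR from baseline:

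- **Visits:** Days 2 to 7, 10 and 14.
- **Terms:** treatment, visit, treatment-by-visit, baseline RR, baseline-by-visit, and the SAP 8.6.1 fixed effects. Protocol 13.5.3 names only treatment and baseline; the extra terms match the SAP's other models.
- **Estimation:** unstructured covariance, Kenward-Roger degrees of freedom and the fallback sequence of SAP 8.6.3.7. With eight visits the unstructured matrix has 8 × 9 / 2 = 36 parameters, so the fallback should be written in.
- **Output:** pairwise adjusted differences with 95% CIs at Days 3, 7, 10 and 14, on the ITT and PP populations, as SAP 8.6.3 requires for secondary endpoints.

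If description alone was intended, add an entry with the reason to SAP section 9, and check the section against Protocol 13.4.2 and 13.5.3 for the other departures at the same time.

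The cost is one model and one table per population on data already collected, or one section 9 entry. No visit, assessment or sample size changes.
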